8.1.5 Response Review

All radiologic reads will be performed by radiologists with expertise in the evaluation of tumor size by RECIST or particular response criteria used for evaluation of response in the particular tumor type.

8.2 Antitumor Effect

When part of standard of care, specific tumor markers may be measured and if measured will be recorded but tumor response for solid tumors will be based in RECIST criteria.

8.3 Hematologic Tumors

Antitumor Effect for Hematologic measures will be evaluated using existing standard Hematologic Response Criteria and will be defined prior to the initiation of therapy.

8.4 Neuro-oncology Tumors

Antitumor effect for Neuro-oncology tumors will be evaluated using the RANO Criteria {Wen, 2010 #8}.

8.5 Patient Reported Outcomes

Baseline patient health literacy will be measured using a three item Health Literacy Scale. Quality of Life will be evaluated using the PROMIS-29 with the 4 point Anxiety Subscale. To measure patient's satisfaction with their decision to pursue next generation sequencing and subsequent therapy, the 5 item Satisfaction with Medical Decision Scale, will be used.

9.0 Adverse Events List and Reporting Requirements

Adverse Events for Off-Label Therapies

The adverse events associated with the targeted or off-label therapeutic agents will vary. These will be outlined to the patient by the treating physician. As per WFCCC standard of care, patients will be provided with a document that explains the adverse events associated with the medication prescribed.

Reporting of Unanticipated Problems, Adverse Events or Deviations

Any unanticipated problems deviations or changes will be promptly reported by the principal investigator or designated member of the research team to the IRB and sponsor or appropriate government agency if appropriate.

9.1 Adverse Event Characteristics

- **CTCAE term (AE description) and grade:** The descriptions and grading scales found in the revised NCI Common Terminology Criteria for Adverse Events (CTCAE) version 5.0 will be utilized for AE reporting. All appropriate treatment areas should have access to a copy of the CTCAE version 5.0. A copy of the CTCAE version 5.0 can be downloaded from the CTEP web site (<http://ctep.cancer.gov>).
- **‘Expectedness’:** AEs can be ‘Unexpected’ or ‘Expected’ for expedited reporting purposes only.
- **Attribution of the AE:**
 - Definite – The AE is **clearly related** to the study treatment.
 - Probable – The AE is **likely related** to the study treatment.
 - Possible – The AE **may be related** to the study treatment.
 - Unlikely – The AE is **doubtfully related** to the study treatment.
 - Unrelated – The AE is **clearly NOT related** to the study treatment.

9.2 DSMC SAE Reporting Requirements

The Data Safety Monitoring Committee (DSMC) is responsible for reviewing SAEs for WFCCC Institutional studies as outlined in [Appendix D](#). All Adverse Events that occur during protocol intervention and are coded as either 1) unexpected grade 4, 2) unplanned inpatient hospitalization ≥ 24 hours (regardless of grade), or grade 5 (death) must be reported to the DSMC using the SAE consol in WISER.

All WFBCCC Clinical Protocol and Data Management (CPDM) staff members assisting a Principal Investigator in investigating, documenting and reporting an SAE qualifying for DSMC reporting are responsible for informing a clinical member of the DSMC as well as the entire committee via the email notification procedure of the occurrence of an SAE.

9.3 WFUHS IRB AE Reporting Requirements

Any unanticipated problems involving risks to subjects or others and adverse events shall be promptly reported to the IRB, according to institutional policy. Reporting to the IRB is required regardless of the funding source, study sponsor, or whether the event involves an investigational or marketed drug, biologic or device. Reportable events are not limited to physical injury, but include psychological, economic and social harm. Reportable events may arise as a result of drugs, biological agents, devices, procedures or other interventions, or as a result of questionnaires, surveys, observations or other interactions with research subjects.

All members of the research team are responsible for the appropriate reporting to the IRB and other applicable parties of unanticipated problems involving risk to subjects or others. The Principal Investigator, however, is ultimately responsible for ensuring the prompt reporting of unanticipated problems involving risk to subjects or others to the IRB. The Principal Investigator is also responsible for ensuring that all reported unanticipated risks to subjects and others which they receive are reviewed to determine whether the report represents a change in the risks and/or benefits to study participants, and whether any changes in the informed consent, protocol or other study-related documents are required.

Any unanticipated problems involving risks to subjects or others occurring at a site where the study has been approved by the WFUHS IRB (internal events) must be reported to the WFUHS IRB within 7 calendar days of the investigator or other members of the study team becoming aware of the event.

Any unanticipated problems involving risks to subjects or others occurring at another site conducting the same study that has been approved by the WFUHS IRB (external events) must be reported to the WFUHS IRB within 7 calendar days of the investigator or other members of the study team becoming aware of the event.

Any event, incident, experience, or outcome that alters the risk versus potential benefit of the research and as a result warrants a substantive change in the research protocol or informed consent process/document in order to insure the safety, rights or welfare of research subjects.

10.0 Pharmaceutical Information

10.1 Pharmaceutical Accountability

The targeted off-label chemotherapeutic or immunotherapy agents are commercially available. Their description, use, preparation, administration, storage and stability parameters are outlined in the package insert. Disposal of remaining portions of the agents should be done per the Wake Forest Waste Stream.

11.0 Data Management

Informed consent document	EPIC
Patient Demographics and clinical data	WISER/OnCore, REDCap
Current Medications List	WISER/OnCore
NGS Result	NGS Database
Patient Withdrawal Form	WISER/OnCore
Adverse Events Log	WISER/OnCore
Vitals	WISER/OnCore
30 day Treatment Follow-up Form	WISER/OnCore
Evaluation of Best Overall Response	WISER/OnCore
Off-Study Form	WISER/OnCore
Study Medication Form	REDCap
PROMIS 29	REDCap
Satisfaction with Medical Decision Scale	REDCap
Patient Reported Outcome-Demographics	REDCap
Telephone Follow up Form	REDCap
Health Literacy Questionnaire	REDCap

12.0 Confidentiality and Privacy

One risk inherent in this project is the loss of confidentiality. Confidentiality will be protected by collecting only information needed to assess operational outcomes and maintaining all study information in a secure manner. Data will be collected on an identifiable level. Following data collection, the data will be kept indefinitely. Data access will be limited to registry staff (Investigators, CPDM staff, and patient navigators). Data and records will be kept password protected, in OnCore (WISER), REDCap and the NGS database. No reference to any individual participant will appear in reports, presentations, or publications that may arise from the collection of this data. The data could be used for a research study. Data will only be given to the research study by the registry staff upon an IRB approval. The Registry staff will serve as honest brokers of the data. All data provided for research will be completely deidentified.

13.0 Data Safety and Monitoring

The principal investigator will be responsible for the overall monitoring of the data of participants.

14.0 Statistical Considerations

14.1 Introduction

It should be noted that the primary analyses for this protocol are examining whether the process of using next generation sequencing methods to identify a potential treatment for patients who have failed previous therapies have any clinically beneficial effects. The goal is not to evaluate a particular treatment per se, but rather an approach to assign a treatment to patients using next generation sequencing methods.

14.2 Analysis of Primary Objective

The primary objective of this non-randomized, single-arm pragmatic trial is to estimate the progression-free ratio as defined by the duration of time from start of treatment to the time of progression divided by the duration of time from the last treatment received pre-trial to the time of progression on that treatment. Those that die before progression or are lost to follow-up will be non-evaluable for the primary objective. The median progression-free ratio will be estimated with the range and a two-sided Wilcoxon Signed Rank test will be calculated to see if the PFS ratio is different from 1.0.

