2.0 Objectives

2.1 Primary Objective

- 2.1.1 To estimate the progression-free ratio, as defined by the progression-free survival time on study treatment divided by the progression-free survival time on the last treatment received by patient, for an identified actionable mutation, who will be treated with an off-label treatment off label therapy based on a simplified selection methodology using the NGS results.

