8.1.4 Survival Outcomes

Progression-Free Survival is defined as the duration of time from the start of treatment to the time of progression, death, or date of last contact; those lost to follow-up will be censored.

Progression-Free Ratio is defined as the duration of time from start of treatment to the time of progression divided by the duration of time from the last treatment received pre-trial to the time of progression on that treatment. Those that die before progression or are lost to follow-up will be non-evaluable for the primary objective.(Cirkel et al., 2016)

Overall Survival is defined as the duration of time from the start of treatment to date of death or date of last contact; those lost to follow-up will be censored.

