14.4 Power and Sample Size

This trial is powered to detect differences in the progression-free ratio for those with actionable mutations identified by NGS results and then treated with a targeted therapy. A hypothesized PFS ratio larger than 1.3 would suggest that the targeted therapy is doing better than the previous treatment received (not targeted), and we assume a null hypothesis PFS ratio of 1.0 (no difference). Using pilot data seen in Von Hoff et al, we assume a conservative standard deviation of 1.71. With 269 evaluable participants, we have 80% power to detect differences in PFS ratio from 1.0 to 1.3, assuming a two-sided Wilcoxon test with level of significance equal to 0.05. This does assume the actual underlying distribution is normal, but powers for a non-parametric Wilcoxon test. ("PASS 16 Power Analysis and Sample Size Software," 2018) As those that die before progression or are lost to follow-up will be non-evaluable for the primary objective, we conservatively allow for 20% non-evaluable. Therefore, we plan to recruit 337 total patients in this trial.

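### The primary PFS-ratio analysis keeps only patients with an observed progression, dropping deaths and censored patients contrary to the plan's own PFS definition; the bias can be material, but its net direction is unknown

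*Combined protocol and SAP*

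**What the plan says.** Objective 2.1.1 describes the ratio as "progression-free survival time on study treatment divided by the progression-free survival time on the last treatment received by patient". Section 8.1.4 defines PFS as running "to the time of progression, death, or date of last contact; those lost to follow-up will be censored". On that definition death is an event and a loss is censored.

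The endpoint that is analysed differs. Sections 5.1.1, 8.1.4 and 14.2 define it as "duration of time from start of treatment to the time of progression divided by the duration of time from the last treatment received pre-trial", where the second period ends when the disease progressed under the earlier therapy, so a progression date is needed in both terms. Section 14.2 adds: "Those that die before progression or are lost to follow-up will be non-evaluable for the primary objective". The analysis is then "The median progression-free ratio will be estimated with the range and a two-sided Wilcoxon Signed Rank test will be calculated" against 1.0, with no censoring method.

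The plan does not say how a patient still progression-free at analysis is handled, and it gives no data cut-off for the primary analysis. Section 14.4 allows for 20% non-evaluable patients without splitting them into deaths and losses.

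**The concern.** Whether a patient enters the primary analysis depends on what happened after treatment began. Three groups leave:

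- **Lost to follow-up.** Progression is seen only if it comes before the loss, so the patients who remain have shorter times to progression. Excluding losses lowers the median ratio.
- **Still progression-free at analysis.** The text does not name this group. Its exclusion follows from the definition, since there is no progression date to divide. It acts in the same direction.
- **Dead before progression.** Under 8.1.4 these are PFS failures. Eligibility admits ECOG up to 3 and life expectancy just over 6 weeks, so some may come early. Excluding early deaths removes small ratios and raises the median.

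At stake is the only primary estimate and its test. The median and the signed-rank test would describe patients who lived to a documented progression, not the treated population named in 2.1.1. Censored information would be used in the secondary Kaplan-Meier analysis of PFS (14.3) and discarded in the primary one.

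**Working it through.** **1. The plan's sample size reproduces.** Inputs from 14.4: difference 0.3, SD 1.71, two-sided 0.05, power 80%. A one-sample t-test needs n = 257. Multiplying by π/3 for the Wilcoxon test under normality gives 257 × 1.0472 = 269.1, the plan's 269. Then 269 / 0.80 = 336.25, rounded up to 337. So 337 − 269 = 68 patients are expected to be non-evaluable. The sample size is not at fault.

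**2. How far 68 exclusions could move the median.** Take the plan's normal model with the evaluable median at 1.30, and let L of the 68 lie below the all-patient median and the rest above. Then q = ((337 + 1)/2 − L) / (269 + 1), and the all-patient median is 1.30 + 1.71 × Φ⁻¹(q).

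| L below | q | All-patient median |
|---|---|---|
| 0 | 169/270 = 0.626 | 1.85 |
| 17 | 152/270 = 0.563 | 1.57 |
| 34 | 135/270 = 0.500 | 1.30 |
| 51 | 118/270 = 0.437 | 1.03 |
| 68 | 101/270 = 0.374 | 0.75 |

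These are worst-case limits, not expectations: up to about 0.55 either way, against a design effect of 0.3.

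**3. Censored patients only.** Assumptions, not from the documents: lognormal times, prior median 4 months, true median ratio 1.30, log SD 0.9 on study and 0.8 prior, correlation 0.3, and uniform accrual over 30 months (within the 2 to 3 years of 14.6). A patient is evaluable if progression precedes both cut-off and loss.

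| Cut-off after last entry | Monthly loss | Dropped | Median among evaluable |
|---|---|---|---|
| 6 months | none | 10% | 1.17 |
| 6 months | 2% | 20% | 1.12 |
| 12 months | none | 5% | 1.23 |
| 12 months | 2% | 16% | 1.16 |
| 24 months | none | 1.6% | 1.28 |

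The shortfall at 6 to 12 months runs from (1.30 − 1.23)/0.30 = 23% to (1.30 − 1.12)/0.30 = 60% of the design effect. At 24 months with 2% monthly loss the median is still only about 1.19 to 1.20.

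**4. The same model with early deaths.** Add an assumed 10% of patients dying at a time uniform over 0.3 to 2 months. The target is now the all-patient PFS ratio with death as an event. It does not depend on the cut-off, so its variation below is simulation error.

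| Cut-off, monthly loss | Evaluable median | All-patient PFS ratio |
|---|---|---|
| 12 months, none | 1.22 | 1.15 |
| 6 months, none | 1.17 | 1.15 |
| 12 months, 2% | 1.15 | 1.14 |
| 6 months, 2% | 1.11 | 1.14 |

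The present rule overstates in the first row, understates in the last, and is nearly right in between because the errors offset.

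**5. A second model.** Assumptions: exponential times, prior median 3 months, on-study median 1.3 times that, a 0.5-month floor, and 20% non-evaluable. All-patient against evaluable median: all lost, 1.27 against 1.02; half early deaths and half lost, 1.07 against 1.09; three-quarters early deaths, 1.00 against 1.13; all early deaths, 0.92 against 1.17. Again the mix sets the sign.

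**The case against.** **Follow-up may be long enough.** Section 8.1.2 continues imaging until progression even after treatment stops, and 6.4 follows patients until death. If the sponsor waits, few patients will still be progression-free: the first model without loss gives 1.28 at 24 months and 1.29 at 36. This stands for that group, but no such wait is written into the plan, and waiting does not recover patients lost to follow-up or dead.

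**The exclusion is declared in advance and allowed for.** True. The 20% in 14.4 protects the count of 269, but it does not make those 269 representative.

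**PFS for all patients is already planned.** Section 14.3 gives Kaplan-Meier curves with censoring. That analysis is secondary and does not compare each patient with his or her own prior time.

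**A time-to-progression ratio may be intended.** The source cited in 8.1.4 has that term in its title. Such an endpoint could be coherent, but 2.1.1 says PFS, and even a time-to-progression analysis need not discard patients whose progression has not yet been seen.

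**A reader might infer that the rule simply hides benefit.** The documents do not support a one-way downward bias, because the same sentence excludes deaths, which can act the other way. Nor can one say that the longest observed times are removed. Patients lost early have short observed times; it is their unobserved times to progression that tend to be long. In the exponential model, mean observed time was 4.5 months in both lost and evaluable patients. How many excluded patients had already outlasted their prior PFS also depends on assumed inputs.

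**Conclusion.** The concern holds as a two-sided selection problem. The mismatch between 2.1.1 and the PFS definition on one side, and the evaluability rule in 5.1.1, 8.1.4 and 14.2 on the other, can be read directly from the text and needs no assumption. The exclusion of ongoing patients is an inference from the endpoint definition.

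The size is conditional. The worst-case limits of 0.75 to 1.85 rest on the plan's numbers of patients, SD and normal model, with the evaluable median set at 1.30. The simulated figures rest on assumed times, loss rates, death rates and cut-offs. They show that errors of roughly 0.1 to 0.2 are plausible against a design effect of 0.3, and that either sign is possible. They do not predict the error in this trial. That two opposing biases may offset is no defence, since nothing in the plan makes them do so.

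**What to change.** In 5.1.1, 8.1.4 and 14.2:

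- Build the on-study term from PFS. Death before progression is an event; lost or still progression-free patients are right-censored at the last disease assessment. Section 8.1.4 now uses last contact, so align that wording, because a contact alone does not show absence of progression.
- Restore both groups together. With 10% early deaths in the lognormal model, recovering the censored patients while still dropping deaths gives about 1.30 against an all-patient 1.15. That is further off than the 1.22 of the present rule at 12 months without loss.
- Analyse all treated patients who have a prior PFS time with a censoring-aware paired method. One option is a Kaplan-Meier median of the ratio with a confidence interval, plus a paired Prentice-Wilcoxon test against 1.0. Specify a version that allows censoring in the on-study member of the pair only. Dividing by the prior time also makes censoring on the ratio scale partly dependent, so the Kaplan-Meier median is approximate and the SAP should say so.
- State the data cut-off and how ongoing patients are handled.
- Keep the observed-progressor median and signed-rank test as a sensitivity analysis, and report non-evaluable patients by reason.

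The cost is protocol and SAP wording, a slightly less simple summary and some extra analysis work. The dates required are already collected.

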14.3 Analysis of Secondary and Exploratory Objectives

Response rate will be estimated for all patients with corresponding 95% confidence intervals. Progression-free survival and overall survival times will be displayed using Kaplan-Meier curves with median survival times and confidence intervals. Adverse events will be summarized in incidence tables by type and grade severity for all patients and presented by type of treatment received. For exploratory objectives, the frequency of types of actionable mutations and previous treatment history will be summarized and demographic characteristics presented. Logistic models will be constructed for each type of mutation (yes/no) to preliminarily explore associations with clinical and demographic characteristics. For quality of life and patient satisfaction outcomes, changes over time will be assessed using a repeated measures ANOVA, with any between time associations utilizing Tukey adjustment for post-hoc comparisons. Transformations and/or non-parametric approaches will be considered for any outcomes violating parametric assumptions.

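### The primary median progression-free ratio is to be reported with its range and a p-value against 1.0, but with no confidence interval, so its precision is not stated

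*Combined protocol and SAP*

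**What the plan says.** Section 2.1 words the primary objective as estimation: "To estimate the progression-free ratio". Section 14.2 repeats this and gives the whole primary analysis in one sentence: "The median progression-free ratio will be estimated with the range and a two-sided Wilcoxon Signed Rank test will be calculated", the test being of a ratio different from 1.0.

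Sections 5.1 and 8.1.4 define the ratio but give no interval. Section 14.4 gives power rather than precision: "With 269 evaluable participants, we have 80% power to detect differences in PFS ratio from 1.0 to 1.3". The test there is two-sided at the 0.05 level. The same section also supplies a second reference value: "A hypothesized PFS ratio larger than 1.3 would suggest that the targeted therapy is doing better than the previous treatment received".

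Intervals are planned elsewhere. For one secondary outcome, section 14.3 states: "Response rate will be estimated for all patients with corresponding 95% confidence intervals". It treats the time-to-event outcomes in the same way: "Progression-free survival and overall survival times will be displayed using Kaplan-Meier curves with median survival times and confidence intervals". The PFS interval there concerns time on study treatment, not the ratio to the previous treatment.

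**The concern.** An estimate needs a measure of its own uncertainty. The range is the smallest and largest individual ratio. It describes patients rather than the median, and it grows with sample size while the median becomes better known.

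The p-value speaks only to 1.0. Followed as written, the primary result would be a median, two extreme values and that p-value. A reader could not tell whether the data fit a ratio of 1.3, or exclude it, or fit only values slightly above 1.0. In a single-arm trial that asks whether a treatment-selection approach helps, that is the main thing the estimate should show.

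**Working it through.** **Inputs.** From 14.4: 269 evaluable, 337 recruited, null 1.0, alternative 1.3, SD 1.71, normal distribution, two-sided alpha 0.05, power 80%, 20% non-evaluable. Our assumption: a lognormal alternative, because ratios cannot be negative. A normal distribution with mean 1.3 and SD 1.71 puts about 22% of ratios below zero.

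**1. The plan's sample size.** A one-sample t-test for a difference of 0.3 with SD 1.71 needs 257. Multiplying by π/3 for the Wilcoxon test under normality gives 257 × 1.047 = 269.1. Then 269 / 0.80 = 336.25, rounded up to 337. Both stated figures reproduce.

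**2. Interval ranks.** The distribution-free interval for a median takes its ranks from Binomial(n, 0.5). At n = 269 these are the 118th and 152nd ordered ratios, with exact coverage 96.2%. The next pair inward (119th and 151st) falls to 94.9%.

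**3. Plan's own assumption: normal, SD 1.71, true median 1.3.**
- Large-sample half-width: 1.96 × 1.71 × √(π / (2 × 269)) = 0.26.
- Simulated average order-statistic interval: about 1.03 to 1.57, a width of about 0.54.
- Simulated average range: about -3.6 to 6.2, a width of about 9.7. The negative end comes from the normal assumption.

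**4. Lognormal, median 1.3.** Ratio SD = 1.3 × exp(s²/2) × √(exp(s²) − 1). Setting this to 1.71 gives log SD s ≈ 0.80.
- SE of the log median: √(π/2) × 0.8 / √269 = 0.061. The factor is exp(1.96 × 0.061) = 1.13, so the large-sample interval is 1.15 to 1.47.
- Simulated order-statistic interval: about 1.15 to 1.48.
- Range: about 0.14 to 12.

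**5. Range against interval as n changes (lognormal, log SD 0.8).** The typical maximum is 1.3 × exp(0.8 × z), where z is the normal quantile at 0.5^(1/n). The typical minimum is 1.3 × exp(−0.8 × z). The interval uses the large-sample formula of step 4.

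| n | z | Range | 95% interval |
|---|---|---|---|
| 50 | 2.20 | 0.22 to 7.6 | 0.98 to 1.72 |
| 269 | 2.80 | 0.14 to 12 | 1.15 to 1.47 |
| 1000 | 3.20 | 0.10 to 17 | 1.22 to 1.38 |

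The two move in opposite directions.

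**6. Does the interval agree with the test?** The order-statistic interval concerns the median. A signed rank test on the raw ratio concerns the median only if ratios are symmetric about it. With simulated lognormal ratios (log SD 0.8, true median 1.1, n = 269), the raw-scale test rejected 1.0 in 99% of trials and the interval excluded 1.0 in 31%; they disagreed in 68%. A second simulation of 3,000 trials under the same set-up gave 70% disagreement with the raw-scale test and 21% with the test on the log ratio.

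**The case against.** The strongest reply is that the decision rests on a test, not on an interval. Section 14.1 asks whether the approach has any benefit, 14.4 powers a test against 1.0, and 14.2 specifies that test. An interval changes neither the sample size nor the data collected. The plan does not forbid one, and it could be computed at reporting. All of this stands, and it is why the point is modest. It does not close the gap: 2.1 and 14.2 both word the objective as estimation, and a method left unnamed can be chosen after the data are seen.

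Three stronger readings are tempting, and the documents do not support them.
- A reader might infer that 1.3 is a success threshold that the interval must clear. Section 14.4 uses it as the powering alternative and as a sign of benefit, and sets no such rule.
- A reader might infer that every secondary endpoint has an interval. Response rate, PFS and OS do; safety is given incidence tables only.
- A reader might take step 6 to show that the primary test or the sample size is wrong. Section 14.4 assumes normal ratios, which are symmetric, so that source of conflict does not arise under the plan's own assumption. It appears under our lognormal one. It bears on how to pair an interval with the test, and test validity at the planned size is not at issue here.

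**Conclusion.** The concern holds as a gap in how the primary estimate is reported. The range cannot stand in for precision: at n = 269 it is about 18 times as wide as the 95% interval under the plan's assumptions (9.7 / 0.54). The interval would be informative. With a true median of 1.3 its average lower limit lies just above 1.0 under the normal assumption (1.03) and clearly above it under the lognormal (1.15).

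These figures rest on exactly 269 independent ratios and an SD of 1.71. The lognormal shape is our assumption. The evaluable number will differ in practice, and 3.1.4 lets a patient re-register after progression, so independence needs one ratio per patient or an allowance for repeats. Severity is modest.

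**What to change.** In 14.2:
- Report the median ratio with a two-sided 95% distribution-free order-statistic interval, with ranks from Binomial(n, 0.5) at the actual evaluable n.
- Read the interval against both 1.0 and 1.3, and keep the range as description only.
- State that the signed rank test is run on the log ratio against 0, so that test and interval both concern the median on a roughly symmetric scale.
- Say that the two can still differ in borderline cases, because the order-statistic interval corresponds to the sign test, which uses less of the data.

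The cost is two or three sentences, with no new data and no change to 269 or 337. The log scale does not call for more patients under the assumption used here: the effect is ln(1.3) / 0.8 = 0.33 SD, against 0.3 / 1.71 = 0.18 SD in 14.4.
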